### Statistical Analysis

Diet and nutrition data will be analysed using Axxya Systems Nutritionist Pro™ Diet Analysis while all statistical analyses are performed with IBM® SPSS® Statistics 23.0. Descriptive methods will be used to demonstrate to describe participant characteristics and the consistency of both groups. Independent t-test or Chi Square will be used to evaluate baseline characteristics of peer intervention

participants compared to control, overall significance of improvement across clinical outcome measures. As this is a RCT involving repeated measures, the ANOVA repeated measures model is applied to observe significant differences between and within the study groups. This includes change in clinical measures of MetS component from baseline, end of trial (3rd month) and follow up (6th month). The magnitude of change in both primary and secondary outcome measures will be estimated and the given 95% confidence intervals with the p value 0.05 was taken as the level of significance.

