## Study Sample

### Sample Size and Power Calculation

The estimated sample size based on earlier similar study (10) on one the study variables, fasting plasma glucose at 95% confidence and 80% power of an anticipated fall in FPG of 1.5 to 1.8 mmol/L. Using an equation to detect changes in a standard parallel-group trial and a 20% drop out rate, the calculated minimum required sample size is 48 participants for each group thus the totalling 96 for both randomized arm.

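### Statistical Analysis puts both a t-test/chi-square and a repeated-measures ANOVA on the between-arm effect for the same MetS measures and does not say which test, ANOVA term or visit decides

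*Combined protocol and SAP*

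**What the plan says.** Under Statistical Analysis, one sentence begins "Independent t-test or Chi Square will be used to evaluate baseline characteristics of peer intervention" and continues, across a page break, "participants compared to control, overall significance of improvement across clinical outcome measures". The t-test/chi-square is therefore attached both to baseline comparability and to improvement in the clinical outcomes.

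The following sentence says that "the ANOVA repeated measures model is applied to observe significant differences between and within the study groups". The plan then specifies that this covers change in the MetS component measures over baseline, month 3 (called the end of the trial) and month 6. The section closes by promising estimates of the size of change with "95% confidence intervals with the p value 0.05 was taken as the level of significance".

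Neither this section nor Outcome Assessment names a primary analysis, says whether the ANOVA group main effect or the group-by-time term answers the question, picks a deciding visit, or says what happens if the analyses disagree.

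**The concern.** The two procedures address the same question, whether the arms differ in improvement on a MetS component, but they are not interchangeable. A t-test on change uses one visit against baseline. The group-by-time term with three visits is a 2-df test of any difference in profile. The group main effect compares averages over all three visits, including the one before treatment.

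They can therefore disagree on the same data. With no deciding analysis fixed in advance, a borderline result could be reported as positive or negative, both consistently with the plan. The nominal 5% then no longer describes the chance of a false claim. This would remain even if the plan named a single endpoint.

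**Working it through.** **Inputs from the documents.** Significance level 0.05 (Statistical Analysis). 48 per arm with 20% dropout (Sample Size and Power Calculation), so 48 × 0.8 = 38.4, about 38 evaluable per arm. Three visits: baseline, month 3, month 6.

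**Assumed, because not given.** Two-sided tests, normal data, independent participants, within-person correlation r between visits of 0.3 to 0.85 (compound symmetry or AR(1)).

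**The plan's own figures.** The only stated error rate is 0.05. The 48 per arm rests on "at 95% confidence and 80% power of an anticipated fall in FPG of 1.5 to 1.8 mmol/L", with no SD given, so it can be neither confirmed nor refuted. It plays no part below beyond fixing the number per arm.

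**Bounds.** For k tests at 0.05, the chance of at least one false positive is at most k × 0.05. If the tests were independent it would be 1 − 0.95^k:
- k = 2: at most 10%; independent 1 − 0.95² = 9.75%
- k = 3: at most 15%; independent 14.3%
- k = 4: at most 20%; independent 18.5%

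Tests on the same data are correlated, so simulation is needed within these bounds.

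**Simulation under no effect.** One endpoint, 20,000 trials per setting, 38 or 48 per arm, Greenhouse-Geisser correction on the interaction. Each of the change t-test, the main effect and the interaction rejects alone in 4.6–5.4%, which reproduces the nominal 5%. A false positive is then counted when any listed test has p < 0.05:

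| Tests that could support a claim | False-positive rate |
|---|---|
| Month-3 raw-value t-test, group main effect | 6.2–8.2% |
| Month-3 change t-test, group × time | 7.2–8.6% |
| Month-3 raw-value t-test, group × time | 8.9–9.8% |
| Month-3 change t-test, group main effect | 9.3–10.1% |
| Both ANOVA terms, no t-test | 9.1–9.9% |
| Month-3 change t-test, both ANOVA terms | 11.6–13.1% |
| Change t-tests at months 3 and 6, both ANOVA terms | 13.3–14.5% |

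The 10.1% entry is Monte Carlo error around the 10% ceiling. A narrower simulation (8,000 trials per setting, compound symmetry, r = 0.3–0.7) gave 11.5–12.2% for the change t-test with both ANOVA terms.

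**How often two tests disagree.** With 38 per arm, compound symmetry and r = 0.3, the change t-test rejects in 4.94%, the interaction in 4.71%, and at least one in 7.35%. Both reject in 4.94 + 4.71 − 7.35 = 2.30%, so exactly one rejects in 7.35 − 2.30 = 5.05%. About one null trial in twenty gives opposite verdicts.

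**Dilution by the main effect.** With no baseline difference and an effect d at both later visits, the main effect estimates (0 + d + d)/3 = 2d/3. Take d = 0.6 SD (assumed), 38 per arm, compound symmetry. The standard error is √(2v/38), and power comes from the noncentral t distribution:

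| Contrast | Effect | v | Power at r = 0.3 | Power at r = 0.7 |
|---|---|---|---|---|
| Month 3, baseline-adjusted | 0.6 | 1 − r² | 0.77 | 0.95 |
| Month-3 change t-test | 0.6 | 2(1 − r) | 0.59 | 0.91 |
| Group main effect | 0.4 | (1 + 2r)/3 | 0.65 | 0.49 |

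The choice of test therefore affects power as well as false positives.

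**The case against.** The strongest reply is that the t-test/chi-square is meant for baseline only. The sentence is ungrammatical, and the ANOVA is introduced as the analysis suited to repeated measures. On that reading the first procedure drops out. But improvement is not a baseline quantity, so this reading has to discard words that are on the page. Even then the deciding ANOVA term is unnamed, and the two terms together give 9.1–9.9%.

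It can also be said that change from baseline points to the group-by-time term, so the main effect is not a true rival. That is a fair inference, and on it the rate with a month-3 change t-test is 7.2–8.6%. The plan does not state it, however, and the reference to differences between groups could equally be read as the main effect.

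A reader might infer that two procedures alone push one endpoint to 12–15%. They cannot: two p-values at 0.05 are capped at 10%. A reader might also add a chi-square on the proportion improved as a further test. With an assumed cut-off of 0.25 SD this gives 13.9–14.8%, but the plan says t-test *or* chi-square, an ordinary choice by type of variable, and defines no responder for any MetS component.

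Finally, the trial is partly described as a feasibility study and promises confidence intervals. Both soften the point, but Study Aims makes the effect on MetS components the primary aim, and the intervals are not tied to a named contrast.

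**Conclusion.** The point holds as an ambiguity with a moderate cost. On its natural reading, Statistical Analysis sets two procedures on the same between-arm question and names no deciding test, term or visit. If either of two p-values could support a claim, the rate for one endpoint is about 6–10%. It is about 12% (up to 13% under AR(1)) if the month-3 change t-test and both ANOVA terms all count, and higher only with further tests such as month-6 t-tests.

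Two limits apply. First, these are rates under a use of the plan that it permits but does not prescribe; a reader might infer that any significant test counts as success, but nowhere is that written. Second, the figures assume independent participants. Randomisation and Treatment Allocation and Randomisation and Blinding both say allocation is by location, and Recruitment Process describes four neighbourhoods, so even a single individual-level test may not hold 5%. The figures show the relative cost of leaving the choice open; they are not this trial's actual error rate.

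**What to change.** In Statistical Analysis, before any outcome data are analysed:

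1. Delete the words after the comma in "participants compared to control, overall significance of improvement across clinical outcome measures", so that the t-test/chi-square serves only to describe the groups at baseline.
2. Add wording such as: *For each clinical outcome, the effect of the intervention will be judged by one contrast: the intervention-minus-control difference at 3 months, adjusted for the baseline value, estimated from the longitudinal model with its 95% confidence interval. The 6-month contrast, the ANOVA group main effect and any other test are supportive and will not be used to claim an effect.*

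Three months is chosen because the section itself treats it as the end of the trial. Naming the visit matters: without it, the 3- and 6-month contrasts would both remain available. With one deciding test the simulated rate returns to about 5%, given independent participants.

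This costs a wording change and no extra data or participants. The downside is that a significant result from a supportive test can no longer be claimed as evidence of effect. The change does not deal with multiplicity across the several MetS components or with allocation by location; those need their own provisions.

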### Recruitment Process

A series of health screening camp were organised around Kulai district located in the south of Malaysia. Johor state was specifically selected due to high prevalence of MetS as reported in Malaysia Adults Nutrition Survey (MANS) (11) (12), Metabolic Syndrome Study Malaysia (MSSM) (13) and National Health and Morbidity Survey 2015 (NHMS) (14). The eligibility screening and recruitment of study participants were conducted in four low to middle income neighbourhoods. The research team provide assistance on identifying potential study participants according to the eligibility criteria (Table 1). If an individual is found to eligible to participate, they will be requested to complete the baseline questionnaire after consenting for their participation.

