### Randomisation and Treatment Allocation

Eligible adults who have consented to participate are matched for age, sex and ethnicity as baseline. To minimised contamination, participants were randomised to either intervention or control group based on their location.

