### *Intervention Group*

Participants residing in the location selected to be intervene will to form at minimum 4 peer groups. This group will receive a continuous three-months, peer-led nutrition and lifestyle behaviour intervention through a series of peer gathering. Two participants from each peer group will be selected as the peer leader (PL). PL will be trained to deliver the content of PERSUADE modules and will be responsible to run a weekly peer gathering with their respective groups for the following three months.

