## Randomisation and Blinding

This study is an open label parallel randomized-controlled trial hence both the research team and participants will not be blinded. However, as the randomisation will be made based on participants location, contamination of participants was minimised.

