### Applicability in Low-to-middle Income Population

The RCT of PERSUADE will be conducted in four low-to-middle class neighbourhoods in Johor which means the participants may be of a lower socioeconomic background than average Malaysians. This is not the exact representation of the entire population as the access to health providers, high quality food availability, health-supportive infrastructure and health knowledge levels are different in the urban as compared to the rural (41, 42). Hence, we are aiming for a better response in these areas due to a higher prevalence of MetS, absent of prevention measures and poor management among individuals with lower socioeconomic background (43). The applicability of peer support in these communities were shown to be well facilitated by the influence of lay health person, simplicity of health message, ability to collective set realistic health goals and the most important is that it is low in cost (43-45). Hence, it will be interesting to investigate responses from those with lower socio-economic status to a peer-led community health program. Eventually, PERSUADE can be an initiative peer support model to be implemented at the low socioeconomic community and suburban area for evaluation of its feasibility and cost-effectiveness. If successful, it can be a precursor for policy makers to initiate more rigorous promotion of such community peer-based programs to other parts of the country.

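### Arms are allocated by location, but the between-arm analysis treats participants as independent and has no location term

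*Combined protocol and SAP*

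**What the plan says.** **Allocation.** Under Randomisation and Treatment Allocation, "participants were randomised to either intervention or control group based on their location". Randomisation and Blinding repeats this and gives the reason: "as the randomisation will be made based on participants location, contamination of participants was minimised". The Intervention Group section shows that arm follows residence: "Participants residing in the location selected to be intervene will to form at minimum 4 peer groups".

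**Number of places.** Recruitment Process: "The eligibility screening and recruitment of study participants were conducted in four low to middle income neighbourhoods". The Discussion agrees: "The RCT of PERSUADE will be conducted in four low-to-middle class neighbourhoods in Johor". The readable text does not say how many locations go to each arm. Figure 2, the flow chart, is not shown and may do so, so this is not counted as an omission.

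**Sample size.** 48 per group, 96 in total, at 95% confidence and 80% power: "Using an equation to detect changes in a standard parallel-group trial and a 20% drop out rate". No design effect is stated.

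**Analysis.** "the ANOVA repeated measures model is applied to observe significant differences between and within the study groups", covering baseline, month 3 and month 6, with 95% confidence intervals and a 0.05 significance level. An independent t-test or chi-square test is also named; that sentence is garbled and mainly concerns baseline. The only dependence recognised is that of repeated visits within a person.

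**The concern.** When whole locations are assigned to an arm, the independent units for comparing arms are locations. The planned tests count people. Any location-level influence on the tested quantity is then part of the arm difference but is missing from its standard error.

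The kind of location variation matters:

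- **Stable differences between neighbourhoods** cancel in change scores and in the group-by-time test. They inflate the ANOVA group main effect and comparisons of follow-up values.
- **Location-by-time variation**, such as a local event or an assessment-day effect, does not cancel. It inflates change-score and group-by-time tests and could be read as a peer-support effect.

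The protocol makes the second kind plausible. Assessments take place at designated peer gatherings, groups share leaders and meet weekly, and allocation by location presupposes that neighbours influence one another.

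Study Aims makes the between-arm effect the primary aim, and the conclusion says the feasibility RCT is also meant to show effectiveness. A false positive would therefore fall on the main result.

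**Working it through.** **1. The plan's own figure.** The sample-size section gives no standard deviation, so 48 per group cannot be reproduced. Working backwards with n = 2(1.96 + 0.84)² SD²/δ² and division by 0.8 for dropout, 48 (38 evaluable) needs an SD of about 2.33 mmol/L if δ = 1.5, or about 2.80 if δ = 1.8. Neither SD is in the documents, and the formula has no term for clustering.

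**2. Inputs.**

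- From the protocol: 48 per arm, 20% dropout, two-sided 5% level, three visits, four neighbourhoods.
- Evaluable participants: 48 × 0.8 = 38.4, taken as 38 per arm.
- Assumed: allocated locations are the four neighbourhoods, split 2 v 2, with 38/2 = 19 evaluable in each.
- Assumed: ICC of 0, 0.01, 0.02, 0.05 or 0.10.

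**3. Approximate check.** Design effect DE = 1 + (19 − 1) × ICC. The true level of an unadjusted test is about 2[1 − Φ(1.96/√DE)]. At ICC 0.05, DE = 1.90 and the level is 2[1 − Φ(1.422)] = 15.5%. At ICC 0.10, DE = 2.80 and the level is 24.2%.

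**4. Simulation under no treatment effect** (300,000 trials per ICC for the t-test, 100,000 for the ANOVA). For the ANOVA, ICC means location-by-time variance divided by itself plus the within-person residual variance; the within-person correlation is 0.6.

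| ICC | t-test on an endpoint or change | 95% CI coverage | Group-by-time ANOVA | Location-mean t-test, 2 df |
|---|---|---|---|---|
| 0 | 4.9% | 95.1% | 5.0% | 5.0% |
| 0.01 | 7.1% | 92.9% | 8.1% | 5.0% |
| 0.02 | 9.2% | 90.8% | 11.1% | 5.0% |
| 0.05 | 15.8% | 84.2% | 20.9% | 5.1% |
| 0.10 | 24.9% | 75.1% | 35.5% | 5.0% |

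The within-person correlation matters little: at ICC 0.05, values of 0.4 and 0.8 give group-by-time rejection of 21.1% and 21.2%. A separate simulation with 20 evaluable per location and the same ICC on level and change gave 7.9, 11.5, 22.4 and 38.3% for group-by-time at ICC 0.01 to 0.10.

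**5. Stable location differences only.** With 5% or 10% of single-visit variance between locations, group-by-time rejects 5.1% or 4.9% and the month-3 change t-test 5.0% in both cases. The group main effect rejects 19.3% or 29.6%.

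**6. A 1 v 3 split.** With 38 evaluable per arm, the individual-level t-test rejects about 8% at ICC 0.01 and 30% at ICC 0.10. The pooled-variance location-mean test rejects 2.6 to 4.0% across ICC 0 to 0.10, so it is conservative.

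**7. Precision of a location-level analysis, 2 v 2.**

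- Expected interval width relative to plan = t(0.975, 2) × 0.8862 × √DE / [t(0.975, 74) × 0.9966]. At ICC 0 this is 4.303 × 0.8862 / (1.993 × 0.9966) = 1.92.
- At ICC 0.01, 0.02, 0.05 and 0.10 it is 2.09, 2.24, 2.65 and 3.21.
- A standardised effect of 0.651 has 80% power at 38 v 38 under individual randomisation. On 2 df (noncentral t) its power is 36, 32, 29, 23 and 17% at ICC 0, 0.01, 0.02, 0.05 and 0.10.

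**The case against.** The strongest reply is that the size of the error is unknown. The plan directs the ANOVA at change from baseline, and stable neighbourhood differences leave change and group-by-time tests at 5%. Inflation there needs correlated change, for which the documents give no figure. This stands as a limit on the percentages, which are illustrative. It does not justify a model that assumes the correlation is zero.

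'Location' is not defined in the readable text. Equating it with the four neighbourhoods, and splitting them 2 v 2, are assumptions. The 1 v 3 case makes the individual-level test worse, so the conclusion does not depend on the split. It does show that the location-mean test holds almost exactly 5% only for equal-sized 2 v 2, and errs on the conservative side under 1 v 3.

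Participants are matched on age, sex and ethnicity. That may reduce stable differences, but it does not remove location-by-time variation.

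Finally, the protocol calls this a feasibility trial. That tempers the consequence without removing it, because the between-arm effect is the stated primary aim. The choice of month 3, and the supportive status of a mixed model, are secondary to the main correction.

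**Conclusion.** The concern holds. Allocation is by location, the analysis is by individual, and nothing in the plan connects the two. Under any positive within-location correlation of the tested quantity, the nominal 5% level, the 95% coverage and the 80% power are not met, and the error favours false positives. For 2 v 2 locations of 19, true error runs from about 7 to 25% (t-test) and 8 to 36% (group-by-time) over ICC 0.01 to 0.10; with no correlation it is 5%. The mismatch follows directly from the text. The percentages rest on the assumed ICC, the assumed split and the reading of location as neighbourhood.

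**What to change.** 1. Describe the trial as cluster-randomised by location, and state what a location is and how many are in each arm.
2. For each metabolic syndrome component, make the primary between-arm estimate the difference in location-mean change from baseline at one time point. Month 3, which the plan calls the end of the trial, is the natural choice, with month 6 secondary. Give a 95% interval on degrees of freedom from the number of locations (2 if 2 v 2). If both visits were primary, the chance of at least one false positive would be about 9 to 10% (simulated 9.3 to 9.7%).
3. Treat any mixed model with a random location effect as supportive, and keep the location term and its degrees of freedom when its variance is estimated as zero. That happened in 27 to 63% of simulated trials; reverting to the individual test in those trials gave 6.4% error at ICC 0.05 and 7.2% at 0.10. A fixed location term is no remedy, because location is nested within arm.
4. Report the observed ICC of change, present the between-arm comparison as exploratory with estimates and intervals, and make no efficacy claim from an individual-level p below 0.05.
5. Withdraw the 80% power statement for this design.
6. If there is only one location per arm, location and treatment are fully confounded; present the comparison as descriptive only.

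**Cost.** No new participants or data are needed, since location is known from allocation. The price is the wider interval and lower power shown in step 7 of the working. Recruiting more people in the same four locations would not restore the degrees of freedom; more locations would be needed for useful power. The 2-df test also assumes roughly normal location means and controls error for each component separately; multiplicity across components is a separate matter.

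### The repeated-measures ANOVA ignores allocation by location and isolates no arm difference at any one visit; a named month-3 contrast tested at location level is needed, and it will not have 80% power

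*Combined protocol and SAP*

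**What the plan says.** The Statistical Analysis section states that "the ANOVA repeated measures model is applied to observe significant differences between and within the study groups", and adds: "This includes change in clinical measures of MetS component from baseline, end of trial (3rd month) and follow up (6th month". An independent t-test or chi-square is assigned to baseline comparison and also to "overall significance of improvement across clinical outcome measures". Estimation is promised in general terms: "The magnitude of change in both primary and secondary outcome measures will be estimated", with 95% confidence intervals. The section does not say which term tests treatment, whether the intervals are between arms, which visit is primary, or how missing visits are handled. It has no baseline covariate and no location term.

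Under Randomisation and Treatment Allocation, "participants were randomised to either intervention or control group based on their location", after participants are "matched for age, sex and ethnicity as baseline". Randomisation and Blinding repeats that allocation follows location. Under Recruitment Process, "recruitment of study participants were conducted in four low to middle income neighbourhoods". The number of locations per arm is not given, and the Intervention Group section refers to the intervention location in the singular. The sample size rests on "fasting plasma glucose at 95% confidence and 80% power of an anticipated fall in FPG of 1.5 to 1.8 mmol/L", with a standard parallel-group equation and 20% dropout, giving 48 per group. No SD, intraclass correlation or design effect is stated.

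**The concern.** There are two faults. First, whole locations are allocated but participants are analysed as independent. Differences between neighbourhoods in diet, income or care then enter the arm comparison while the standard error leaves them out. Matching on age, sex and ethnicity makes a metabolic gap between locations less likely but does not exclude one.

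Second, the primary aim is a comparison with control, and neither obvious reading of the ANOVA gives an arm difference at a stated visit. The group-by-time term only asks whether the arm difference varies over three visits. The between-group term includes baseline, where no effect can exist. Tests within an arm do not compare the arms. A significant result could therefore be reported as an intervention effect when it reflects place, a month-6 pattern or change over time in one arm.

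**Working it through.** **Inputs.** From the documents: 48 per group, 20% dropout, 80% power, 5% level, four neighbourhoods, three visits. Assumed, because not stated: two-sided test, two locations per arm, correlation between visits ρ = 0.5 or 0.7 (shown as 0.5/0.7), and location variances as given below, with participant variance within location set to 1.

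**The plan's own figure.** 48 × 0.80 = 38.4, so 38 evaluable per arm; in reverse, 38/0.80 = 47.5, rounded up to 48. Without an SD the number cannot be rebuilt from mmol/L. Solving for 80% power with 38 per arm gives a standardised effect d = 0.651 (t-test; 0.643 by normal approximation). All results below are in SD units.

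**1. What the ANOVA terms test (location set aside).**
- Group-by-time: noncentrality = (n/2) × Σ(arm difference − mean difference)² / (1 − ρ). Arm differences of (0, d, d) and of (0, 0, d) both give a sum of (2/3)d². So 19 × (2/3) × 0.651² / (1 − ρ) = 10.7/17.9, and power on F(2, 148) is 84%/97% in both cases. The test cannot tell an effect sustained from month 3 from one present only at month 6.
- Between-group main effect: the mean of (0, d, d) is (2/3)d, and of (0, d, 0) is (1/3)d. At ρ = 0.5 power is 63% and 21% respectively.

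**2. Ignoring location.** With 19 evaluable per location the design effect is 1 + 18 × ICC. The error rate is 2[1 − Φ(1.96/√DE)].

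| ICC | DE | Error, formula | Error, simulated |
|---|---|---|---|
| 0.01 | 1.18 | 7.1% | 7.2% |
| 0.05 | 1.90 | 15.5% | 15.7% |
| 0.10 | 2.80 | 24.1% | 25.0% |

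A second simulation (10,000 runs) separates a stable location effect from one that varies by visit:

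| Location / location-by-visit variance | Group-by-time | Month-3 change | Baseline-adjusted |
|---|---|---|---|
| 0.05 / 0.01 | 10.8%/15.9% | 8.9%/12.3% | 11.7%/12.6% |
| 0.02 / 0.005 | 7.9%/10.4% | 7.1%/8.9% | 8.0%/8.5% |

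**3. Location-level test (2 df), variances 0.05/0.01.** SE of the adjusted difference = √[(1−ρ)² × 0.05 + (1+ρ²) × 0.01 + (1−ρ²)/19] = 0.254/0.215. The 95% half-width is 4.303 × SE = 1.09/0.93 SD. Power is 31%/39%, and simulated error 5.1%/4.9%. For change, SE = √[0.02 + 2(1−ρ)/19] = 0.270/0.227 and power is 29%/36%. On the ICC scale, power runs from 17% (ρ = 0, ICC 0.10) to 61% (ρ = 0.8, ICC 0.01).

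**4. Random-location mixed model.** With Satterthwaite df, 24 enrolled per location, 10% missing at month 3 and 20% at month 6, error is 5.8%/5.9% and power 52%/61%. The location variance is estimated as zero in 43% of runs. A simplified check (one adjusted outcome, 22 per location, ρ = 0.5) shows what this means. In the 44% of runs with zero variance, error is 13%, the same as ignoring location. In the other runs it is close to 0%. About 92% of rejections under the 0.65 SD effect come from the zero-variance runs.

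**5. Persistent gap.** Baseline adjustment leaves (1 − ρ) of a stable gap: for 0.3 SD, 0.15/0.09 SD. With no effect, the mixed model then rejects 9%/8% of the time adjusted, against 5%/6% for change.

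**6. Missing visits.** With 10% lost by month 3 and 20% by month 6 (assumed), complete cases keep 38.4 per arm instead of 43.2 at month 3, a loss of 9.6 people over both arms. If 10% of the intervention arm and none of the control arm leave after month 3, with odds 2.7 times higher per SD worse change, the complete-case difference in change is overstated by 0.09/0.07 SD (14%/11%). If dropout is alike in both arms there is no such bias.

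**The case against.** The strongest reply is that every magnitude depends on variances, correlations and a 2 v 2 split that the documents do not give, and that the protocol repeatedly describes a feasibility study, for which 80% power is not the standard. The first part stands: the sizes are illustrative. The direction does not depend on them, since any positive location variance inflates the error. The feasibility label does not settle the matter either, because the protocol states a powered sample size, a primary aim against control and a 5% significance level.

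Four stronger readings are tempting, and the documents or the figures do not support them.
- A reader might infer that a mixed model with a random location term puts the error rate right. It does so only on average and approximately. In over 40% of simulated trials it reverts to ignoring location.
- A reader might take the Study Aims section to fix month 3 as the primary visit. There, three months is the length of the intervention. Month 3 is the natural choice because the Statistical Analysis section labels it as the end of the trial, but no visit is designated primary.
- A reader might infer that the plan discards partial follow-up by rule. It is silent; the loss follows from the classical procedure. The Control Group section does commit to two follow-ups over six months.
- A reader might take two locations per arm as given. It is an assumption.

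Clustering within peer groups, in the intervention arm only, is a further unmodelled source. The Intervention Group section gives a minimum of four groups and Peer Leader Selection a minimum of eight; these need reconciling.

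**Conclusion.** The analysis is wrong as written and should be changed. It treats participants as independent under allocation by location, and neither ANOVA term estimates the arm difference at a single visit. With two locations per arm, the nominal 5% error becomes roughly 7%–16% under the illustrative variances, or 7%–25% for ICC 0.01–0.10.

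The location-level test was the one that held 5% throughout the simulations, so it should carry the inference. It relies on roughly normal location means with similar variance in the two arms. A randomisation test is no substitute: a 2 v 2 split has 6 allocations, so its smallest two-sided p-value is 2/6 = 0.33. Power is about 31%–39% with a half-width of 0.9–1.1 SD, or 17%–61% over ICC 0.01–0.10 and ρ up to 0.8. The stated 80% is not delivered by this allocation. If each arm is one location, which the singular wording allows, arm and location are fully confounded and no analysis can separate them.

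**What to change.** In Statistical Analysis, replace the repeated-measures ANOVA as the treatment test:

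- **Contrast.** Name the between-arm difference at month 3 in fasting plasma glucose, the sample-size variable, with its 95% CI. Month 6 and the other measures are supporting.
- **Baseline.** Adjust for the baseline value of the outcome. Report the arm difference in change alongside, because adjustment removes a persistent location gap only in part.
- **Primary inference.** Test baseline-adjusted location means, with 2 df if there are two locations per arm. Estimate the baseline slope from participants within locations, so that it does not use up those df. Give the random-location mixed model with small-sample df as supporting only.
- **Missing visits.** Include everyone with a month-3 value in the month-3 contrast, and state the missing-data assumption.
- **Other tests.** Limit the t-test and chi-square to baseline description. Do not use within-arm tests as evidence of effect.

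State the number of locations per arm. If it is one, present the results as descriptive feasibility estimates. In Sample Size and Power Calculation, state that 80% power assumed individual randomisation and does not hold under allocation by location.

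The cost is wording only, on visits and measures already scheduled. The price is wide intervals and low power, which wording cannot recover. As a guide, the same 76 evaluable participants spread over about 12 locations would give 81% power at ρ = 0.5 and ICC 0.01; at ICC 0.05 even 16 locations give 79%.
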